3. STUDY DESIGN

Figure 1 Study design overview – maternal participants

GA = Gestational age; I = immune response; (S)AE = (serious) adverse event; RTI = respiratory tract illness
 Visit 2 may be replaced by Visit 3 in case of premature delivery.

All = all participants

Refer to Protocol Amendment 5 Section 6.3.2 for detailed description of Stage A and Stage B. Refer to Protocol Amendment 5 Section 6.3.2.1.1 for additional description of the Stage A sub-cohort.

[figure not shown]
Solicited events will be evaluated for all participants in **Stage A only**

* Any pregnancy-related event of special interest identified after Visit 4 should also be reported.

In addition to the monthly contacts between Visit-2 and the Delivery visit, additional not pre-specified visits and contacts (any desired frequency) can be made between Visit-2 and the Delivery visit, as per investigator’s or maternal participant’s discretion.

As from protocol Amendment 4, blood samples will be collected at delivery from all maternal participants. Placental samples will be collected at delivery from all maternal participants, if feasible

Due to the stop on study enrolment and vaccination, nasal swab samples will no longer be collected from any maternal participant and no MA-RTI assessment visit will be performed, but the MAEs associated with an RTI will continue to be reported, as applicable.

Figure 2 Study design overview – infant participants

I = immune response; (S)AE = (serious) adverse event; RTI = respiratory tract illness

Stage A + Stage B – all participants:

*If cord-blood was not collected at delivery/birth, a blood sample should be collected from the infant **within 72 hours post birth**. Applies to all participants in Stage A and Stage B.

**Any Neonatal AE of specific interest identified *after* Day 43 should also be reported.

An additional recommended safety contact may be performed 8-days post-birth if deemed necessary by the investigator or by the parent/LAR(s).

Due to the stop on study enrolment and vaccination, blood samples will no longer be collected at V2-NB, V3-NB or V4-NB.

- Study Type: self-contained
- Study Duration: Approximately 10 to 11 months (including the screening visit) for maternal participants; approximately 1 year after birth for infant participants.
- Blinding is as described in [Table 2](#) and [Table 3](#).
- Randomized intervention allocation: A minimum of 4600 and up to a maximum of 10,000 pregnant women (maternal participants) will be randomly assigned (2:1) to receive the investigational vaccine or control (placebo) at Visit 1. Randomization will take place in 2 sequential stages, A and B. Approximately 4,600 maternal participants will be randomized into Stage A. Stage B will only start after the last participant is randomized in Stage A. Participants in stage A will be randomized (12:2:2:2:6:1:1:1 ratio) to be in the RSV group, in one of the 3 infant blood sampling sub-cohorts and receiving the investigational vaccine (RSVMAT_BS1 (Day 43), RSVMAT_BS2 (Day 121), RSVMAT_BS3 (Day 181)), in the Control group, or in one of the 3 infant blood sampling sub-cohorts receiving placebo (Control_BS1 (Day 43), Control_BS2 (Day 121), Control_BS3 (Day 181)). Randomization will be via the automated internet-based system (SBIR). The system's randomisation algorithm of maternal enrolment will use a minimisation procedure accounting for maternal age at the time of the study intervention (18-34, 35-39, ≥ 40 years of age), gestational age at the time of the study intervention ($24^{0/7}$ - $28^{0/7}$; $28^{1/7}$ - $34^{0/7}$), and center. Minimisation factors will have equal weight in the minimisation algorithm.
- Study (intervention) groups are described in [Table 2](#) and [Table 3](#)
- Data collection: standardized Electronic Case Report Form (eCRF). E-Diaries will be used to collect solicited event data.

- Safety monitoring will be conducted by an unblinded Independent Data Monitoring Committee (IDMC) and by an unblinded Safety Review Team*. The analyses for IDMC safety evaluations will be described in a separate SAP for IDMC.

** Due to the safety signal observed, the study was fully unblinded to ensure the safety of the participants.*

CONFIDENTIAL

212171 (RSV MAT-009)
Statistical Analysis Plan Amendment 5

Table 2 Study groups, sub-cohorts, interventions, and blinding foreseen in the study: Stage A

Approximately 4,600 maternal participants will be randomized during Stage A.

Study groups	Maternal participants (M)				Infant participants (I)			Study Groups for Randomization	Blinding			
	~Number	Age in Years (Min/Max)	Intervention name	Maternal Blood Sampling Sub-cohorts	Infant Blood Sampling sub-cohorts	(Allocation 12:2:2:2:6:1:1:1)	Screening		M only	M + I	I only	
				Name	~Number	Name	~Number					
RSV_MAT	~3,067	18-49	RSV_MAT	RSV_MAT_0	~2,040	RSV_MAT_0	~2,040	RSVMAT_0	•	•	•	
		18-49	RSV_MAT	RSV_MAT_I	~1020	RSV_MAT_BS1	~340	RSVMAT_BS1				•
						RSV_MAT_BS2	~340	RSVMAT_BS2				•
						RSV_MAT_BS3	~340	RSVMAT_BS3				•
Control	~1,533	18-49	Control	Control_0	~1020	Control_0	~1020	Control_0	•	•	•	
		18-49	Control	Control_I	~510	Control_BS1	~170	Control_BS1				•
						Control_BS2	~170	Control_BS2				•
						Control_BS3	~170	Control_BS3				•

Control = Placebo; Infant sub-cohorts are abbreviated “BS1;” “BS2;” BS3” and correspond to visits 2-NB (Day 43), 3-NB (Day 121) and 4-NB (Day 181), respectively.

RSVMAT_0 and Control_0 = maternal and infant participants who are not in a sub-cohort for immune response assessment.

RSVMAT_I and Control_I = maternal sub-cohorts for immune response assessment.

RSVMAT_BS1, _BS2, _BS3 = infants born to women in the RSVMAT_I sub-cohort and evaluated for immune response at the designated timepoint (D43, D121 or D181).

Control_BS1, _BS2, _BS3 = infants born to women in the Control_I sub-cohort evaluated for immune response at the designated timepoint (D43, D121 or D181).

Table 3 Study groups, sub-cohorts, interventions, and blinding foreseen in the study: Stage B

Approximately a maximum of 5,400 maternal participants may be randomized during Stage B.

Stage B will only start after the last participant is randomized in Stage A.

Study groups	Number of maternal participants	Age of maternal participant at enrolment (Min/Max)	Intervention name	Study groups for randomization (Allocation 2:1)	Blinding		
					Maternal participants Only (Screening)	Maternal participants V1-C1 Infant participants V1-NB – V4NB (double-blind)	Infant participants only Contact 2-NB – V5-NB (double blind)
RSV_MAT	~3,600	18 – 49 years	RSV_MAT	RSV_MAT	•	•	•
Control	~1,800	18 – 49 years	Control	Control	•	•	•

4. ANALYSIS SETS

4.1. Definition

For the purpose of the analysis the following analysis sets are defined.

Table 4 Maternal Participants

Analysis Set	Description
Enrolled	All maternal participants who completed the informed consent process and signed the informed consent form.
Exposed	All maternal participants who received the study intervention. The allocation in a group is done in function of the administered intervention.
Per Protocol - Immunogenicity	All maternal participants who received the study intervention to which they were randomised and have post-vaccination data minus participants with protocol deviations that lead to exclusion.
Solicited Safety – Stage A only	All maternal participants in the Exposed Set who have solicited safety data

Table 5 Infant participants

Analysis Set	Description
Exposed	Infants live-born to exposed maternal participants, whose parents/LARs completed the informed consent process and signed the informed consent form.
Per Protocol - Immunogenicity	All infant participants in the Exposed set minus those who (a) were born less than 4 weeks post- maternal participant vaccination and/ or (b) have protocol deviations that lead to exclusion.
Full Analysis - Efficacy	All infant participants in the Exposed set.
Modified Full Analysis - Efficacy	All infant participants in the Exposed set who were born after at least 4 weeks of vaccination.
Per Protocol - Efficacy	All infant participants in the Modified Full Analysis – Efficacy set minus those who have protocol deviations that lead to exclusion.

CONFIDENTIAL

212171 (RSV MAT-009)
Statistical Analysis Plan Amendment 5

Table 6 Overview of analysis sets and exclusion codes

Determined in mother or infant	Code	Description	Maternal analysis set				Infant analysis set				
			Enrolled	Exposed	Per Protocol - Immunogenicity	Solicited Safety	Exposed	Per Protocol - Immunogenicity	Modified Full Analysis - Efficacy	Full Analysis - Efficacy	Per Protocol - Efficacy
Mother	800, 800#	Fraudulent Data	Y	Y	Y	Y	Y	Y	Y	Y	Y
Mother	900, 900#	Invalid informed consent	Y	Y	Y	Y	Y	Y	Y	Y	Y
Mother	1030, 1030#	Study vaccine not administered		Y	Y	Y	Y	Y	Y	Y	Y
Mother	1040.Vx+*, 1040#	Administration of concomitant vaccine(s) forbidden in the protocol			Y			Y			Y
Mother	1050, 1050#	Randomisation failure			Y			Y			Y
Mother	1060, 1060#	Randomisation code was broken ^a			Y			Y			Y
Mother	1070, 1070#	Mother got vaccinated with the correct vaccine but incorrect volume			Y			Y			Y
Mother	1070, 1070#	Vaccination not according to protocol (site of injection, route of administration, wrong replacement of study treatment administered)			Y			Y			Y
Mother	1070, 1070#	Study treatment not prepared as per protocol (e.g. reconstitution)			Y			Y			Y
Mother	1070, 1070#	Other deviations related to wrong study treatment/ administration/dose			Y			Y			Y

CONFIDENTIAL

212171 (RSV MAT-009)
Statistical Analysis Plan Amendment 5

Determined in mother or infant	Code	Description	Maternal analysis set				Infant analysis set				
			Enrolled	Exposed	Per Protocol - Immunogenicity	Solicited Safety	Exposed	Per Protocol - Immunogenicity	Modified Full Analysis - Efficacy	Full Analysis - Efficacy	Per Protocol - Efficacy
Mother	1070, 1070#	Study treatment administered while contraindicated			Y			Y			Y
Mother	1080, 1080#	Vaccine temperature deviation			Y			Y			Y
Mother	1090, 1090#	Expired vaccine administered			Y			Y			Y
Mother	1160	No post-vaccination solicited safety data- Stage A participants only				Y					
Mother	2010, 2010#	Protocol violation (inclusion/exclusion criteria)			Y			Y			Y
Mother	2040.Vx+*, 2040#	Administration of any medication/product forbidden by the protocol			Y			Y			Y
Mother	2050.Vx+*, 2050#	Intercurrent medical conditions/concomitant medications which are exclusionary as per protocol			Y			Y			Y
Mother	2060.Vx+*, 2060#	Concomitant infection related to the vaccine which may influence the immune response			Y			Y			Y
Mother	2070.Vx+*, 2070#	Concomitant infection not related to the vaccine but may influence the immune response			Y			Y			Y

CONFIDENTIAL

212171 (RSV MAT-009)
Statistical Analysis Plan Amendment 5

	Code	Description	Maternal analysis set				Infant analysis set				
			Enrolled	Exposed	Per Protocol - Immunogenicity	Solicited Safety	Exposed	Per Protocol - Immunogenicity	Modified Full Analysis - Efficacy	Full Analysis - Efficacy	Per Protocol - Efficacy
Determined in mother or infant											
Mother	2090.Vx	Participant did not comply with blood sample schedule			Y						
Mother	2100.Vx	Serology result not available (immunogenicity sample collected but invalid/no result)			Y						
Mother	2120.Vx	Obvious incoherence or abnormality or error in the data			Y						
Mother	2130.Vx	Testing performed on serology samples not aligned with ICF			Y						
Mother	2110.Vx	Immunogenicity sample collected but GSK decided not to test			Y						
Infant	800	Fraudulent Data					Y	Y	Y	Y	Y
Infant	900	Invalid informed consent					Y*	Y	Y	Y	Y
Infant	2010	Protocol violation (inclusion/exclusion criteria)						Y			Y
Infant	2050.Vx	Intercurrent medical conditions which are exclusionary as per protocol						Y			Y
Infant	2090.Vx	Participant did not comply with blood sample schedule						Y			

CONFIDENTIAL

212171 (RSV MAT-009)
Statistical Analysis Plan Amendment 5

	Code	Description	Maternal analysis set				Infant analysis set				
			Enrolled	Exposed	Per Protocol - Immunogenicity	Solicited Safety	Exposed	Per Protocol - Immunogenicity	Modified Full Analysis - Efficacy	Full Analysis - Efficacy	Per Protocol - Efficacy
Determined in mother or infant											
Infant	2100.Vx	Serology result not available (immunogenicity sample collected but invalid/no result)						Y			
Infant	2120.Vx	Obvious incoherence or abnormality or error in the data						Y			
Infant	2130.Vx	Testing performed on serology samples not aligned with ICF						Y			
Infant	2131.Vx	Testing performed on nasal samples not aligned with ICF									Y
Infant	2110.Vx	Immunogenicity sample collected but GSK decided not to test						Y			
Infant	2040.Vx+, 2040#	Administration of any medication/product forbidden by the protocol (leading to elimination from PPS-E and PPS-I)						Y			Y
Infant	2140Vx+	Administration of any medication/product forbidden by the protocol (leading to elimination from PPS-I)						Y			
Infant	2240	Administration of any medication/product forbidden by the protocol (leading to elimination from PPS-E)									Y

CONFIDENTIAL

212171 (RSV MAT-009)
Statistical Analysis Plan Amendment 5

Determined in mother or infant	Code	Description	Maternal analysis set				Infant analysis set				
			Enrolled	Exposed	Per Protocol - Immunogenicity	Solicited Safety	Exposed	Per Protocol - Immunogenicity	Modified Full Analysis - Efficacy	Full Analysis - Efficacy	Per Protocol - Efficacy
Infant	2060.Vx, 2060#	Concomitant infection related to the vaccine which may influence immune response						Y			Y
Infant	2070.Vx, 2070#	Concomitant infection not related to the vaccine but may influence immune response						Y			Y
Infant	3100	Birth is less than 4 weeks post-vaccination						Y	Y		Y

* in case a mother withdraws consent or does not consent for the baby, we still report SAEs/AESIs for the infants if collected

.Vx indicates participants whose data will be eliminated from a specific endpoint/visit

[figure not shown]
.Vx+ indicates participants whose data will be eliminated from a specific endpoint/visit onwards

Y indicates exclusion

[figure not shown]
Carry forward elimination from mother to infant

^a Randomization code was broken (1060, 1060#) does not apply to the unblinding of all participants during the study due to the stop on study enrollment and vaccination and the study was fully unblinded

4.2. Criteria for eliminating data from Analysis Sets

4.2.1. Elimination from Exposed Set (ES)

4.2.2. Elimination from Modified Full Analysis Set for Efficacy (modified FAS-E)

4.2.2.1. Excluded Infants from Modified Full Analysis Set for Efficacy

An infant will be excluded from the modified FAS efficacy analysis under the following conditions:

Code	Condition under which the code is used	Visit (timepoints) where the code is applicable
800, 800#	Fraudulent data	All
900, 900#	Invalid informed consent	All
1030#	Study vaccine not administered	All
3100	Birth is less than 4 weeks post-vaccination	All

Carry forward elimination from mother to infant

4.2.3. Elimination from Full Analysis Set for Efficacy (FAS-E)

4.2.3.1. Excluded Infants from Full Analysis Set for Efficacy

An infant will be excluded from the FAS efficacy analysis under the following conditions:

Code	Condition under which the code is used	Visit (timepoints) where the code is applicable
800, 800#	Fraudulent data	All
900, 900#	Invalid informed consent	All
1030#	Study vaccine not administered	All

Carry forward elimination from mother to infant

4.2.4. Elimination from Per protocol analysis set for Efficacy (PPS-E)**4.2.4.1. Excluded Infants from Per protocol analysis set for Efficacy (PPS-E)**

A participant will be excluded from the PPS efficacy analysis under following conditions:

Code	Condition under which the code is used	Visit (timepoints) where the code is applicable
800, 800#	Fraudulent data	All
900, 900#	Invalid informed consent	All
1030#	Study vaccine not administered	All
3100	Birth/Delivery is less than 4 weeks post-vaccination	All
1040#	Administration of concomitant vaccine(s) forbidden in the protocol	All
1050#	Randomisation failure	All
1060#	Randomisation code was broken	All
1070#	Mother got vaccinated with the correct vaccine but containing an incorrect volume	All
1070#	Vaccination not according to protocol (site of injection, route of administration, wrong replacement of study treatment administered)	All
1070#	Study treatment not prepared as per protocol (e.g. reconstitution)	All
1070#	Other deviations related to wrong study treatment/administration/dose	All
1070#	Study treatment administered while contraindicated	All
1080#	Vaccine temperature deviation	All
1090#	Expired vaccine administered	All
2010, 2010#	Protocol violation (inclusion/exclusion criteria)	All
2040*	Administration of any medication/product forbidden by the protocol (leading to elimination from PPS-E and PPS-I)	All
2240*	Administration of any medication/product forbidden by the protocol (leading to elimination from PPS-E)	All
2040*	Administration of any medication/product forbidden by the protocol (leading to elimination from PPS-E and PPS-I)	All
2050.Vx*	Intercurrent medical conditions/concomitant medications which are exclusionary as per protocol	All

Code	Condition under which the code is used	Visit (timepoints) where the code is applicable
2050#*	Maternal intercurrent medical conditions which are exclusionary as per protocol	All
2060#* 2060*	Concomitant infection related to the vaccine which may influence immune response	All
2070#* 2070*	Concomitant infection not related to the vaccine but may influence immune response	All
2120.Vx	Obvious incoherence or abnormality or error in data	All
2131.Vx	Testing performed on nasal samples not aligned with ICF	All

.Vx indicates participants whose efficacy data will be eliminated from a specific endpoint

Carry forward elimination from mother to infant

* Attribution of these elimination codes to participant need CRDL review of individual listing

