**9.3.1. Criteria for elimination from analysis**

The Statistical Analysis Plan (SAP) will provide a complete list of criteria for elimination from the analysis sets. Criteria may include, but are not limited to, those in Sections [9.3.1.1](#) and [9.3.1.2](#).

**9.3.1.1. Intercurrent medical conditions and concomitant medications / products / vaccines that may lead to elimination of a participant (maternal/infant) from per-protocol analyses (efficacy/immunogenicity)****9.3.1.1.1. Maternal participants**

- Any of the medications listed in Section [5.2.1.2](#) if administered up to Delivery (Visit 3), except corticosteroids for fetal lung maturation administered after study vaccination.

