**9.3.1.1.2. Infant participants**

- **For the efficacy analyses:**
  - Systemic immunosuppressants or other immune-modifying drugs administered chronically (i.e. for more than 14 consecutive days).
    - For corticosteroids, this will mean prednisone or equivalent,  $\geq 0.5$  mg/kg/day.
    - Topical steroids are allowed.
    - Inhaled steroids are allowed if used in accordance with local labelling information (e.g. for budesonide).
  - RSV-specific immunoglobulins at any time during the study
- **For the immunogenicity analyses:** Immunoglobulins and/or any blood or plasma derivatives administered up to Day 43 post birth (Visit 2-NB), or Day 121 post birth (Visit 3-NB), or Day 181 post-birth (Visit 4-NB), depending on the infant's assigned sub-cohort for blood sampling.

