**9.3.1.1.3. Maternal and Infant participants**

- Diagnosis during the study with an immunological disorder or occurrence during the study of a condition (other than the study pregnancy) capable of altering immune response. For evaluation of immunogenicity endpoints in maternal and infant participants, this includes RSV infection confirmed either locally or by GSK Biologicals during the specified analysis interval.
- Any investigational or non-registered product (drug or vaccine) other than the study vaccine/product administered during the specified analysis interval.

**9.3.1.2. Other situations that may lead to elimination of a participant (maternal / infant) from per-protocol analyses (efficacy/immunogenicity)**

- Protocol violation(s) linked to the inclusion/ exclusion criteria, including maternal age at Visit 1 (study intervention).
- Study intervention not administered as specified by the protocol.
- Failure to comply with the post-dose immunogenicity blood sampling schedule at a given time-point (Table 3).

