2050.Vx*	Intercurrent medical conditions which are exclusionary as per protocol	All
2060.Vx#+* 2060.Vx+*	Concomitant infection related to the vaccine which may influence immune response	All
2070.Vx#+* 2070.Vx+*	Concomitant infection not related to the vaccine but may influence immune response	All
2090.Vx	Participants did not comply with blood sample schedule 
 • For PPS at Visit 1/Day 1 check the interval of day 1 BS -0/+3 days; • For PPS at Visit 2/Day 43 post-birth, check the interval of day 43 BS -12/+18 days; • For PPS at Visit 3/Day 121 post-birth, check the interval of day 121 BS -10/+20 days; • For PPS at Visit 4/Day 181 post-birth, check the interval of day 181 -15/+20 days 	Visit 1-NB/Birth Visit 2-NB/Day 43 post-birth ^a Visit 3-NB/Day 121 post-birth ^a Visit 4-NB/Day 181 post-birth ^a
2100.Vx	Serological results not available (immunogenicity sample collected but invalid/no result)	Visit 1-NB/Birth Visit 2-NB/Day 43 post-birth ^a Visit 3-NB/Day 121 post-birth ^a Visit 4-NB/Day 181 post-birth ^a
2120.Vx	Obvious incoherence or abnormality or error in the data	Visit 1-NB/Birth Visit 2-NB/Day 43 post-birth ^a Visit 3-NB/Day 121 post-birth ^a Visit 4-NB/Day 181 post-birth ^a
2130.Vx	Testing performed on serology samples not aligned with ICF	Visit 1-NB/Birth Visit 2-NB/Day 43 post-birth ^a Visit 3-NB/Day 121 post-birth ^a Visit 4-NB/Day 181 post-birth ^a
2110.Vx	Immunogenicity sample collected but GSK decided not to test	Visit 1-NB/Birth Visit 2-NB/Day 43 post-birth ^a Visit 3-NB/Day 121 post-birth ^a Visit 4-NB/Day 181 post-birth ^a
3100	Birth is less than 4 weeks post-vaccination.	All

* Attribution of these elimination codes to participant need CRDL review of individual listing

Carry forward elimination from mother to infant

Vx+ indicates participants whose immunogenicity data will be eliminated from a specific visit onwards;

Vx indicates participants whose immunogenicity data will be eliminated from a specific visit.

^a As per Protocol Amendment 4, infant blood samples will not be collected at V2-NB, V3-NB and V4-NB. 2090.Vx, 2100.Vx, 2120.Vx, 2130.Vx will not be applicable to infant participants whose blood samples are not collected under Protocol Amendment 4.

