For RSV infection the sponsor will analyse nasal swabs by quantitative reverse transcription polymerase chain reaction (qRT-PCR) for the presence of RSV A/B. A positive (RSV A or B) test result constitutes a case of RSV infection.

In the event the collection of a nasal swab for testing by the sponsor is impossible, results from locally collected samples, tested with locally approved tests, may also be considered for the determination of a case of RSV infection.

For the analysis of RTI episode, a new RTI episode will be defined as any occurrence of cough and/or difficulty in breathing with an interval of at least 7 consecutive days without cough and/or difficulty in breathing since the last/previous episode of RTI.

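### The per-protocol efficacy set can drop infants for the infection that makes them RSV endpoint cases, because SAP code 2060 has no exemption for confirmed RSV

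*SAP*

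**What the plan says.** SAP 5.2.1 bases the primary efficacy analysis on the modified FAS-E. It adds analyses on the FAS-E and the PPS-E to complement it.

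SAP 4.2.4.1 lists the conditions that exclude an infant from the PPS-E. One row carries the mother's carried-forward code (2060#) and the infant's own code (2060), both applicable at all timepoints: "Concomitant infection related to the vaccine which may influence immune response". Table 6 marks the infant row for exclusion from both the PPS-I and the PPS-E. A companion code, 2070, covers infections not related to the vaccine. The only qualifier on 2060 is an asterisk: "Attribution of these elimination codes to participant need CRDL review of individual listing".

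SAP 9.2.2 makes confirmed RSV infection part of the RSV-LRTI definition, and severe RSV-LRTI must first meet that definition. On confirmation it states: "A positive (RSV A or B) test result constitutes a case of RSV infection".

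Protocol 9.3.1 leaves the complete list of elimination criteria to the SAP ("Criteria may include, but are not limited to, those in Sections" 9.3.1.1 and 9.3.1.2). Section 9.3.1.1.3 covers conditions that can alter the immune response, for per-protocol analyses generally, and then adds: "For evaluation of immunogenicity endpoints in maternal and infant participants, this includes RSV infection confirmed either locally or by GSK Biologicals". The infant efficacy list in 9.3.1.1.2 names chronic immunosuppressants and "RSV-specific immunoglobulins at any time during the study". It does not name RSV infection.

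**The concern.** An exclusion triggered by the outcome itself is not a protocol-deviation rule. If code 2060 means RSV infection, the event that makes an infant a primary endpoint case also makes that infant removable from the PPS-E. The PPS-E could lose cases, and its VE would be biased if removal differed by arm. The reviewer of the individual listings is given no criteria, in a study that is fully unblinded.

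Timing adds to this. SAP 7.1 says the 6-month analysis, which covers the primary efficacy endpoints, has already taken place and is labelled for public disclosure. The final analysis it lists names secondary but not primary efficacy, so no later planned step would bring a misapplied flag to light.

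**Working it through.** **Does 2060 mean RSV?** The SAP does not define the code, so this is an inference. Three things support it:
- the vaccine antigen is the RSV F protein (protocol 2.1);
- code 2070 takes the infections not related to the vaccine;
- RSV is the only infection that protocol 9.3.1.1.3 names.

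**Is there an exemption?** None appears in 4.2.4.1, in Table 6 or its footnotes, or in SAP section 8. The SAP does write one elsewhere: footnote a of Table 6 says that "Randomization code was broken (1060, 1060#) does not apply to the unblinding of all participants during the study". It also has separate medication codes for PPS-I only (2140) and PPS-E only (2240). The means to limit a code exist and were not used for 2060.

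**Does it contradict the protocol?** It differs in scope. The protocol names RSV infection for immunogenicity endpoints only, and the SAP does not repeat that limit. It is not a breach, because 9.3.1 lets the SAP add criteria.

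**Notation.** The infant's code is 2060.Vx in Table 6, appears with the onwards suffix in Table 8 ("2060.Vx#+* 2060.Vx" followed by the plus sign and asterisk), and has no visit suffix in 4.2.4.1. Suffixes are dropped in the same way for 2040 and 2070, so this is notation to align and not evidence of a wider efficacy rule.

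**Illustrative size.** The plan gives no figure to reproduce. Inputs:
- Infants at the Day 43 analysis (protocol 2.3): 5235, of whom 3496 active, so 5235 − 3496 = 1739 control.
- Attack rates from the table titles in the protocol's List of Tables: any severity 1.5%, 3%, 6%; severe 0.5%, 1%, 2%. That these are 6-month control-arm rates is an assumption.
- VE at the design targets in protocol 4.2.5: 50% any severity, 70% severe.
- PPS-E assumed to hold 80–100% of these infants.

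Expected cases: control c = 1739 × p; vaccine v = 3496 × p × (1 − VE). At 3%, c = 52.2 and v = 52.4, total 104.6. At 1% severe, c = 17.4 and v = 10.5, total 27.9.

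| Endpoint | Control rate | Eligible cases, 100% of infants | 80% of infants |
|---|---|---|---|
| Any severity | 1.5% | 52.3 | 41.8 |
| Any severity | 3% | 104.6 | 83.7 |
| Any severity | 6% | 209.2 | 167.4 |
| Severe | 0.5% | 13.9 | 11.2 |
| Severe | 1% | 27.9 | 22.3 |
| Severe | 2% | 55.8 | 44.6 |

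VE = 1 − (v/nv)/(c/nc), where nv and nc are the infants in each arm. The 95% interval is log RR ± 1.96 × √(1/v + 1/c − 1/nv − 1/nc). Removed infants leave both numerator and denominator.

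Equal removal in both arms (100% of infants):

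| Share of cases removed | Any severity at 3%: VE (95% CI) | Severe at 1%: VE (95% CI) |
|---|---|---|
| None | 50.0% (27.0–65.8) | 70.0% (35.6–86.0) |
| 10% | 50.1% (25.5–66.5) | 70.0% (32.9–86.6) |
| 25% | 50.2% (22.8–67.9) | 70.1% (27.6–87.6) |
| 50% | 50.4% (14.9–71.1) | 70.1% (11.8–89.9) |

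Removal in one arm only, any severity at 3%:

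| Share removed in that arm | Placebo only: VE | Vaccine only: VE |
|---|---|---|
| 5% (about 3 infants) | 47.4% | 52.5% |
| 10% (about 5) | 44.6% | 54.9% |
| 20% (about 10) | 37.9% | 59.9% |

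If every confirmed case were removed, both arms would have zero cases and VE would be undefined.

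**The case against.** The strongest defence is that the harmful reading defeats the analysis the SAP plans. If every confirmed RSV infection triggered 2060, the PPS-E would contain no RSV-LRTI cases, which nobody would intend. The label also fits a breakthrough case poorly, since it speaks of a concomitant infection that may affect the immune response. The same label appears in the PPS-I tables, where it makes sense, so it may simply have been carried over. Read with protocol 9.3.1.1.2 and 9.3.1.1.3, the documents point towards keeping RSV cases, and the individual review stands between the code and any removal.

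Much of this stands. The meaning of 2060 is inferred, removal is not mechanical, nothing shows that any case was removed, and the removal shares above are hypothetical. But a likely intention is not a written rule. The text says excluded, and a review without criteria in an unblinded study is discretion, not an exemption. Partial removal is the more plausible error, and it would not show itself as an empty table would.

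Two further points are fair. Restricting 2060 to the PPS-I is safe only if the code covers nothing but RSV, because the first part of 9.3.1.1.3 supports excluding other immune-altering conditions from per-protocol efficacy. And a SAP edit now has little forward effect on primary efficacy, so the check of past flags matters more.

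**Conclusion.** The concern holds. The infant's own code 2060 is a stated PPS-E exclusion with no exemption for RSV endpoint cases, and the protocol names RSV infection for immunogenicity endpoints only. That much is plain from the text. The consequence rests on reading 2060 as RSV and on the code having been attributed to cases, which the documents neither show nor rule out.

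The reach is limited to the PPS-E analysis of the two primary efficacy endpoints. The modified FAS-E, the FAS-E and the secondary infant efficacy analyses do not use the code. No efficacy hypothesis is tested and VE is descriptive. Within the PPS-E the potential effect is material under the assumed rates: equal removal mainly costs precision, while a handful of removals in one arm shifts the estimate by several percentage points. It should be fixed.

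**What to change.** State in SAP 4.2.4.1 and Table 6, in a footnote like the one for code 1060, that an infant's confirmed RSV infection does not eliminate the infant or the case from the PPS-E. This wording is safe even if 2060 also covers other infections. If the sponsor confirms that the code means RSV alone, restricting the infant's own 2060 to the PPS-I does the same job.

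Then check the 2060 flags used in the completed 6-month PPS-E analysis and report any removals by group. Rerun the PPS-E only if an infant was removed, and label that rerun as done after unblinding.

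Align the 2060 suffixes across Table 6, Table 8 and 4.2.4.1. The maternal carry-forward 2060# is a separate matter and needs only to be reconciled with protocol 9.3.1.1.3 and with Table 7, which applies the maternal code at Day 31 and Delivery.

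The cost is one SAP line or footnote and a flag check, plus a rerun only if needed. No new data are required.
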